11.4 Interim Analysis

No interim analysis is planned for this study. An assessment of the diagnosis of pneumonia will be confirmed by a panel of independent experts reviewing the clinical data under blinded conditions to ensure that a minimum of 10 documented pneumonia cases has been achieved.

11.5 Sample Size Justification

The sample size proposed is based on the primary clinical variable, ie. occurrence of pneumonia which is estimated at a 10% occurrence of pneumonia in colonized patients under mechanical ventilation. This reflects international clinical experience with patients under mechanical ventilation and respiratory tract colonization with *P. aeruginosa* (Expert Meeting, Paris, November 15, 2001). The majority of the recruited centres can provide historical figures between 10 and 15% occurrence when no prevention therapy to *P. aeruginosa* is applied. This percentage however may fluctuate depending on country, hospital, department, patient subpopulations, season, and specific nosocomial strains at time of study.

The conservative figure of 10% has been elected which should correspond to recruiting 100 patients in the placebo study group for achieving 10 pneumonia cases. Depending on the degree of clinical efficacy

elicited by azithromycin treatment, the total patient figure may thus fluctuate between 200 assessable patients (10 pneumonia in placebo group, 0 pneumonia in active group, i.e. complete protection) and 100 patients (5 pneumonia in placebo group, 5 pneumonia in active group, i.e. no protection). This is based as described above on Fischer's exact test for the primary analysis variable, i.e. occurrence of pneumonia (two-sided, $p=0.10$, 10% in placebo group).

12. ETHICAL AND LEGAL ASPECTS

12.1 Good Clinical Practice

The procedures set out in this study protocol, pertaining to the conduct, evaluation, and documentation of this study, are designed to ensure that the sponsor and investigator abide by the principles of the good clinical practice (GCP), ICH guidelines, FDA or national guidelines as appropriate, and the ethical principles laid down in the current revision of the Declaration of Helsinki.

12.2 Delegation of Investigator Responsibilities

The investigator should ensure that all persons assisting with the trial are adequately informed about the protocol, any amendments to the protocol, the study treatments, and their trial-related duties and functions.

The investigator should maintain a list of subinvestigators and other appropriately qualified persons to whom he or she has delegated significant trial-related duties.

12.3 Subject Information and Informed Consent

Before being admitted to the clinical study, the subject must consent to participate after the nature, scope, and possible consequences of the clinical study have been explained in a form understandable to him or her. An informed consent document that includes both information about the study and the consent form will be prepared and given to the subject. This document will contain all elements required by national law and Sponsor's requirements. The document must be in a language understandable to the subject and must specify who informed the subject. In majority of countries, the person who informs the subject must be a physician.

After reading the informed consent document, the subject must give consent in writing. The subject's consent must be confirmed at the time of consent by the personally dated signature of the subject and/or the subject's legally authorized representative such as a close family member in the event the patient is unable to follow or understand clearly the explanations provided and by the personally dated signature of the person conducting the informed consent discussions.

If the subject or the subject's legally authorized representative is unable to read, oral presentation and explanation of the written informed consent form and information to be supplied to subjects must take place in the presence of an impartial witness. Consent must be confirmed at the time of consent orally and by the personally dated signature of the subject or by the personally dated signature of the subject's legally authorized representative. The witness and the person conducting the informed consent discussions must also sign and personally date the consent document.

A copy of the signed consent document must be given to the subject or the subject's legally authorized representative. The original signed consent document will be retained by the investigator. In accordance with the ICH and national recommendations a copy of the signed informed consent document will be kept by the sponsor in a sealed envelope which will have been closed, identified, and signed on site by the investigator. This envelope can only be opened by the investigator or by the authorities at their request.

The investigator will not undertake any measures specifically required for the clinical study purposes until valid consent has been obtained.

12.4 Confidentiality

Subject names will not be supplied to the sponsor. Only the subject number and subject initials will be recorded in the CRF, and if the subject name appears on any other document (e.g. pathologist report), it must be obliterated before a copy of the document is supplied to the sponsor. Study findings stored on a computer will be filed in accordance with local data protection laws for computerized data. The subjects will be told that representatives of the sponsor, ERC or regulatory authorities may inspect their medical records to verify the information collected, and that all personal information made available for inspection will be handled in strictest confidence and in accordance with local data protection laws.

The investigator will maintain a personal subject identification list (subject numbers with the corresponding subject names) to enable records to be identified.

12.5 Protocol Amendments

Neither the investigator nor the sponsor's representatives will alter this study protocol without obtaining the written agreement of the other. Once the study has started, amendments should be made only in exceptional cases. The changes then become part of the study protocol.

12.6 Approval of the Study Protocol and Amendments

Before the start of the study, the study protocol, informed consent document, and any other appropriate documents will be submitted to the Ethical Review Committee (ERC) with a cover letter or a form listing the documents submitted, their dates of issue, and the site for which approval is sought. Before the study initiation, the sponsor will notify the authorities according to local legal requirements.

Study medication can only be supplied to the investigator after documentation on **all** ethical and legal requirements for starting the study has been received by the sponsor. This documentation must also include a list of the members of the ERC, including their gender, occupation, and qualifications. The opinion given by the ERC should specify the study title, study code, study site, amendment number if appropriate and any other documents reviewed. It must mention the date on which the decision was made and must be officially signed by a committee member, usually the president or secretary to the ERC. In the USA an FDA Form 1572 must be filled.

Before the first subject is enrolled in the study, all ethical and legal requirements must be met.

The ERC and, if applicable, the authorities must be informed of all subsequent protocol amendments, in accordance with the national legal requirements. Amendments must be evaluated to determine whether formal approval must be sought and whether the informed consent document should also be revised.

The investigator must keep a record of all communication with the ERC. This also applies to any communication between the investigator and the authorities.

12.7 Ongoing Information for the Ethical Review Committee (ERC)

If required by legislation or by the ERC, the investigator must submit to the ERC:

- Information on serious or unexpected adverse events as soon as possible
- Periodic reports on the progress of the study if it is requested on the initial reply of the ERC.

12.8 Premature Closure of the Study

The sponsor or the investigator has the right to close this study at any time. As far as possible, this should occur after mutual consultation. The ERC must be informed.

Should the study be closed prematurely, all study materials (completed, partially completed, and blank CRF, study medication, etc.) must be returned to the sponsor, as if the study had been completed.

12.9 Record Retention

The following records must be retained by the investigator until at least 2 years after the last approval of a marketing application in an ICH region and until there are no pending or contemplated marketing authorization in an ICH region, or at least 2 years have elapsed since the formal discontinuation of clinical development of the investigational product. However, as a consequence of international regulatory requirements, the sponsor may request retention for a longer period. These essential documents include:

- Signed informed consent documents for all subjects
- Subject identification code list (must be kept 15 years according to European regulations), screening log (if applicable), and enrollment log
- Record of all communications between the investigator and the ERC
- Composition of the ERC
- Record of all communications between the investigator and sponsor's representatives
- List of subinvestigators and other appropriately qualified persons to whom the investigator has delegated significant trial-related duties, together with their roles and their signatures
- Copies of case report forms and of documentation of corrections for all subjects
- Drug accountability records
- Record of any body fluids or tissue samples retained
- All other source documents (patient records, hospital records, laboratory records, worksheets etc.)
- All other documents as listed in Section 8 of the ICH consolidated guideline on GCP (Essential Documents for the Conduct of a Clinical Trial) or by FDA Guidelines if appropriate (Form 1572 etc.)

However, because of international regulatory requirements, the sponsor may request retention for a longer period of time. The investigator must therefore obtain approval in writing from the sponsor prior to destruction of any records.

Normally, these records will be held in the investigator's archives. If the investigator is unable to meet this obligation, he must ask the sponsor for permission to make alternative arrangements. Details of these arrangements should be documented.

12.10 Liability and Insurance

In accordance with GCP and ICH guidelines, the sponsor has subscribed to an insurance policy covering, in its terms and provisions, its legal liability for injuries caused to participating persons and arising out of this research performed strictly in accordance with the scientific protocol as well as with applicable law and professional standards.

13. STUDY MONITORING AND AUDITING

Monitoring and auditing procedures developed by Quintiles will be followed, in order to comply with GCP guidelines. On-site checking of the case report forms for completeness and clarity, cross-checking with source documents, and clarification of administrative matters will be performed.

13.1 Study Monitoring

The study will be monitored by the sponsor's representatives, by personal visits from the site monitor who will review the case report forms and source documents, supported on occasions by the study manager and clinical pharmacologist. By frequent communications (letter, telephone, and fax), the site monitor will ensure that the investigation is conducted according to protocol design and requirements, and to regulatory guidelines.

All unused study materials are to be returned to the sponsor after the clinical phase of the trial has been completed.

13.2 Source Data Verification and On-Site Audits

The national agency, the ERC, and/or a clinical quality assurance group delegated by the sponsor may request access to all source documents, case report forms, and other study documentation for on-site audit or inspection. Direct access to these documents must be guaranteed by the investigator, who must provide support at all times for these activities.

14. DOCUMENTATION AND USE OF STUDY FINDINGS

14.1 Documentation of Study Findings

A case report form (CRF) will be prepared by the investigator for each study part and carefully reviewed with the sponsor's representatives for adequacy and completeness of parameters listed. All protocol-required information collected during the study for each subject will be entered on the study worksheets or recorded as print outs or graphs (i.e. source documents). All clinical and safety data collected will be entered electronically by the investigator's designated representative, and printed CRF provided. Details of CRF completion and procedure for documentation of corrections will be agreed. Relevant PD data and PK data will be provided as tables. If the investigator authorizes other persons to make entries or corrections in the CRF, the names, positions, signatures, and initials of these persons must be supplied to the sponsor's representatives.

The investigator, or designated representative, should complete the worksheet pages as soon as possible after information is collected, preferably when a study subject is seen for an examination, treatment, or any other study procedure. Any outstanding entries must be completed immediately after the final examination. An explanation should be given for all missing data.

The site monitor will perform a 100 % accuracy check between source documents and CRF and printouts and do random and targeted checking of calculated parameters as estimated appropriate. A source data location list will be prepared and updated during the study. This list will be filed in both the trial master file and the investigator study file. The completed CRF as well as appropriate tables and graphs capturing raw and calculated data must be reviewed and signed by the investigator named in the study protocol or by a designated subinvestigator.

The site monitor will perform a 100 % accuracy check between source documents, tables, laboratory data, printouts etc. and CRF, also performing some random or targeted checking of calculated parameters as estimated appropriate.

The sponsor will retain the originals of all CRFs, 1 set of ECG copies for manual reading if needed, 1 set of ECG copies for archiving purposes, as well as copies of the source documents. The investigator will retain a copy of all CRFs, 1 set of ECG recording (original + copy), and the original source documents.

14.2 Use of Study Findings

All information concerning the product as well as any matter concerning the operation of Anbics AG, such as clinical indications for the drug and other scientific data relating to it, that have been provided by Anbics AG and are unpublished, are confidential and must remain the sole property of Anbics AG. The investigator will agree to use the information only for the purposes of carrying out this study and for no other purpose unless prior written permission from Anbics AG is obtained.

Anbics has full ownership of the original CRFs completed and other documents listed above as part of the study. By signing the study protocol, the investigator agrees that the results of the study may be used for the purposes of national and international registration, publication, and information for medical and pharmaceutical professionals. If necessary, the authorities will be notified of the investigator's name, address, qualifications, and extent of involvement.

The sponsor's representatives will prepare a final report on the study, with the support of the investigator who will perform the statistical and pharmacokinetic evaluation of the data. He will be required to sign a statement that he has read the report and confirms that, to the best of his knowledge, it accurately describes the conduct and results of the study.

The Coordinating Investigator, his delegate or [name] shall have the right to present and to publish the scientific findings from the Study within a reasonable time after termination of the study and

availability of the clinical study report. Circulation of the manuscript among co-authors to achieve consensus should be performed in advance and the manuscript should be submitted to Anbics at least one month in advance for further discussion and approval. Co-authorship will reflect scientific involvement in study design, study performance, and/or analysis. Anbics is entitled to express any demand about the publication in order to protect its commercial interest. Requests and responses will be documented in writing.

15. STUDY DURATION AND DATES

The duration of this study is expected to be approximately 1 year, depending on total of patients recruited (range 120 to 240) to achieve 10 cases of pneumonia for a total between 100 and 200 assessable patients. A study start in November 2002 would enable completion in Autumn 2003 to achieve 200 assessable patients. The actual overall study duration or subject recruitment period may vary.

APPENDIX A

Child Pugh's Score

Clinical and Laboratory Signs	Scoring* by Anomaly		
	1	2	3
Hepatic encephalopathy (stage)	Absent	1 or 2	3 or 4
Ascites	Absent	Moderate	Abundant
Bilirubin (µmol/L)	17 - 34	35 - 51	> 51
Albuminemia (g/L)	> 35	28 - 35	< 28
Prothrombin time (% of normal)	> 70	40 - 70	< 40
Prolongation vs. control (seconds)	< 4	4 - 6	>6

Score by the sum of the points for each sign:

Grade A	5 to 6
Grade B	7 to 9
Grade C	10 to 15

APPENDIX B

Laboratory Safety

Hematology

Hemoglobin total

Hematocrit

RBC

Mean corpuscular hemoglobin (MCH)

Mean corpuscular volume (MCV)

WBC with differential count (neutrophils, lymphocytes, monocytes, eosinophils, basophils)

Platelet count

Prothrombin time (PT)

Activated partial thromboplastin time (aPTT)

Blood chemistry

Fasting glucose

Albumin, total protein

Creatinine

Urea

Sodium, potassium, calcium, chloride

Uric acid

AST, ALT, CPK, AP,

Gamma glutamyl transferase

Total bilirubin

Urinalysis

Macroscopic examination (dipstick) at screening and study completion (Day n or Day 21)

pH

Protein

Glucose

Ketones

Leucocytes

Blood

Urobilinogen

Bilirubin

APPENDIX C

Preparation of Drug Treatment Solutions for i.v. Administration

Material

Sterile pouches containing 250 mL of sterile saline (0.9 % sodium chloride)

Syringes 5 mL

Twin set of labels printed by Quintiles Clinical Supplies (left side to be pasted onto pouch by pharmacist, right side to be torn off by investigator prior to infusion and pasted on CRF)

Pharmacist

The pharmacist will prepare the supplies using the patient schedule provided by the investigator, the patient allocation number and the randomization list provided by the statistical department.

A. For patients allocated to treatment with azithromycin

- Aspirate 4.8 mL sterile water for injection with a 5 mL syringe and add to the lyophilized azithromycin vial
- Shake each vial gently until complete dissolution has taken place (100 mg/mL)
- Check that no particulate matters are left by carefully mirroring the vial against light
- Withdraw with a syringe 3.0 mL from a pouch containing 250 mL of sterile saline and replace by 3.0 mL of reconstituted azithromycin solution at 100 mg/mL solution, leading to a final 250 mL solution at 1.2 mg/mL
- Attach the appropriate study label (left side) with study number, study day and patient allocation number
- Transfer 1, 3 or 6 infusion pouches to the investigator as jointly agreed to cover the needs for 1, 3, or 6 days of treatment, along with the additional labels to be attached onto the CRFs
- Keep all used azithromycin vials to enable compliance monitoring

B. For patients allocated to treatment with placebo

- Use a pouch containing 250 mL of sterile saline
- Attach the appropriate study label (left side) with study number, study day and patient allocation number to each pouch
- Transfer 1, 3 or 6 infusion pouches to the investigator as jointly agreed, along with additional labels to be attached onto the CRFs

Investigator:

- Store the transmitted pouches at room temperature (<30 °C or >86 °F) if for 24 hours, else at 5 °C or 41 °F) for a maximum of 6 days
- If maintained refrigerated, take out the appropriate pouch at least 1 hour prior to drug administration
- Tear off the right part of the label and attach onto the CRF
- Suspend the pouch and connecting line onto the peristaltic pump for a delivery rate of 250 mL / hour
- Record carefully time of infusion start (t=0) and completion (1 hour), ultimately discarding the pouch

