5. STUDY TREATMENTS

5.1 Details of Study Treatments

Treatment

Drug code	ANB 006
INN	Azithromycin (dihydrate) MW 785.0
Dosage form	Glass vials, 10 mL, sterilized Lyophilized azithromycin 500 mg Inactive ingredients (413.6 mg citric acid and sodium hydroxide) Under vacuum
Route	i.v. solution in sterile 0.9% sodium chloride, 250 mL, in sterile pouch Administered as 1 hour infusion (1.2 mg/mL) after reconstitution in 2 steps For details, see Appendix C
Dose	300 mg
Duration	Multiple dose, once a day, for a maximum of 20 days
Manufacturer	Ben Venue Laboratories Inc. Single commercial batch USA The batch number and the expiration date of lyophilized material will be recorded in the Clinical Study Report.
Clinical supplies	No specific release required since commercial batch used without re-packing Study label printed and affixed by Quintiles on each vial

Placebo

Dosage form	Not applicable
Dose	0 mg
Route	i.v. solution of sterile 0.9% sodium chloride, 250 mL, in sterile pouch Administered as 1 hour infusion after reconstitution in 2 steps For details, see Appendix C
Manufacturer	To be purchased locally by each local hospital pharmacy as a single batch The source, batch number and the expiration date of lyophilized material will be recorded in the Clinical Study Report.

Subjects will be administered i.v. from infusion pouches as a solution of 250 mL containing 300 mg azithromycin in saline at 1.2 mg/mL or normal saline (placebo), over 1 hour.

Vials with lyophilized material can be stored at room temperature (30 °C or 86 °F and below). After reconstitution, azithromycin solutions (100 mg/mL and 2 mg/mL) can be stored for 24 hours at or below room temperature (30 °C or 86 °F) or for 7 days if stored under refrigeration (5°C or 41°F).

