5.2 Dosage Schedule

At each study site, the study medication will be prepared by the hospital pharmacist, using the method described in Appendix C, the randomization numbers allocated to the site and the randomization code provided by the independent statistician. The pouches will be infused i.v. by the investigator or his delegate, carefully following the procedures set out in this study protocol. Administration of study drug will be time zero, Day 1 (i.e. t=0 start of infusion) and the i.v. infusion will last 1 hour. Exact date, start

and completion time of infusion will be recorded daily in the case report form (CRF). If a central line is available, the study drug will be preferably infused by that port, avoiding any other concomitant infusion.

Efforts will be made to comply with a 24 hour interval between daily doses for a given patient throughout the treatment period as much as technically feasible. The maximum duration of treatment will be 20 days.

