5.4 Blinding, Packaging, and Labeling

The vials with lyophilized azithromycin will be stored at room temperature (30 °C or 86 °F) or below, under lock, pending preparation by the study site hospital pharmacist, according to study allocation schedule and detailed procedures described in Appendix C procedures for dilution in 2 steps. The investigator will provide the pharmacist in a timely fashion with a precise schedule for treatment days for a given subject (initials and code #) to be treated. Dilution of active drug will be performed with sterile saline 0.9 % purchased at study start by hospital pharmacy (same batch). Placebo will be prepared with the same sterile saline solution. The infusion pouches will be delivered to the investigator at regular intervals during the period as considered most convenient for pharmacy and clinical site (daily, 1, 2 or 3 times a week), providing storage temperature is respected (room temperature up to 24 hours, 5 °C or 41 °F up to 7 days until 1 hour prior to administration). The code will not be discussed or alluded to by the pharmacist, either when discussing with the investigator and his staff, the patient or the monitor to maintain the double blind conditions.

The twin study labels (multilingual as required) for the clinical supplies will be printed for each subject and each study day by Quintiles, the left side label being attached to the infusion pouch by the pharmacist, and the right side label being later detached and affixed to the CRF. The expiry date provided on the labels of both study drugs (azithromycin, saline) will correspond to the date of administration (7 days if pouch stored at 5°C, 1 day if stored at room temperature) and not to the azithromycin batch expiry date. These labels will contain the following information:

Study labels for distribution to investigator

To be attached on pouch

To be attached on CRF

ANB 006 #2001	
Azithromycin or Placebo for i.v. infusion	
Store 5 °C or 41 °F, do not freeze, 250 mL	
Drug exclusively for clinical trial	
Regulatory text (country specific)	
Allocation #	Anbics
Day 1, 2, 3,.....	Zurich
Expiry date.....	Batch.....

ANB 006 #2001	
Allocation #	
Day 1, 2, 3,...	
Date dispensed.....	
Anbics	
Zurich	
Batch.....	

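### Appendix C gives active pouches a 3.0 mL syringe exchange and placebo pouches none, contrary to Section 5.1, and no stated measure masks signs of pouch entry

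*Protocol*

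**What the plan says.** Appendix C sets out two procedures for the pharmacist.

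- **Part A, azithromycin:** after dissolving the vial, "Withdraw with a syringe 3.0 mL from a pouch containing 250 mL of sterile saline and replace by 3.0 mL of reconstituted azithromycin solution". The pouch is then labelled and transferred.
- **Part B, placebo:** "Use a pouch containing 250 mL of sterile saline". The pouch is then labelled and transferred. No withdrawal, injection or sham entry is listed.

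Section 5.1 describes placebo as "i.v. solution of sterile 0.9% sodium chloride, 250 mL, in sterile pouch" and adds "Administered as 1 hour infusion after reconstitution in 2 steps", with a reference to Appendix C for details.

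Section 5.4 says "Placebo will be prepared with the same sterile saline solution". Its other measures bearing on the blind are a pouch label reading "Azithromycin or Placebo for i.v. infusion" in either arm, preparation by the hospital pharmacist, a single expiry-date rule for both products, and "The code will not be discussed or alluded to by the pharmacist".

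On handling, Section 5.2 says "The pouches will be infused i.v. by the investigator or his delegate". Under Appendix C the investigator's side stores the pouches (1, 3 or 6 at a time), tears off the CRF label, hangs the pouch and discards it. This is repeated daily for at most 20 days.

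**The concern.** Followed as written, Appendix C means that every active pouch has been entered by syringe, while no placebo pouch has, so far as the listed steps show. Sections 5.1 and 5.4 and Appendix C name no cover, port seal or matched handling that would hide the difference. If a sign of entry reaches the bedside, the people who could read it are those making the decisions that feed the endpoints.

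Under Sections 6.2 and 7.2.4, diagnostic work-up by BAL, PBS or aspirate follows clinical suspicion at the site. The use of antipseudomonal antibiotics and the timing of extubation are also site decisions. The expert panel is blinded, but it reviews data that the site chose to generate, so it cannot fully undo a difference in work-up between arms. Randomisation is by site in blocks of 4 (Section 5.3), so recognising the arm of some patients would also help staff guess others in the same block.

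**Working it through.** **1. The plan's own figure.** Inputs from Appendix C, part A: 3.0 mL withdrawn, 3.0 mL added at 100 mg/mL, 250 mL pouch.

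- Dose: 3.0 mL × 100 mg/mL = 300 mg.
- Final volume: 250 − 3.0 + 3.0 = 250 mL.
- Concentration: 300 mg / 250 mL = 1.2 mg/mL, as the protocol states.

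Both arms therefore leave the pharmacy at 250 mL, and volume does not reveal the arm.

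**2. The steps side by side.**

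| Step | Active (App. C, A) | Placebo (App. C, B) | Placebo (Section 5.1) |
|---|---|---|---|
| Vial dissolved | yes | no | implied by the two-step wording |
| 3.0 mL withdrawn from pouch | yes | not listed | implied by the two-step wording |
| 3.0 mL injected into pouch | yes | not listed | implied by the two-step wording |
| Study label | yes | yes | – |
| Final volume | 250 mL | 250 mL | 250 mL |

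Syringe entry is the one physical difference in pouch handling that the documents record between the arms.

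**3. Does a stated measure cover it?** The neutral label hides the allocation in print. The shared saline and the equal volume match the contents by source and quantity. Pharmacy preparation and the pharmacist's silence keep the code off the ward. None of these acts on the port or the outer condition of the pouch.

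**4. How sensitive is the primary test?** Sections 11.3 and 11.5 give Fisher's exact test, two-sided, at 0.10, with recruitment stopping at 10 confirmed cases. For a split of *a* placebo and *b* azithromycin cases, the table is [[a, n − a], [b, n − b]] with n patients per arm. I take n = 100, the protocol's upper assessable figure of 200 halved, and n = 75 as an intermediate value.

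| Split (placebo–azithromycin) | p, n = 100 | p, n = 75 |
|---|---|---|
| 9–1 | 0.0185 | 0.0175 |
| 8–2 | 0.1005 | 0.0976 |
| 7–3 | 0.3311 | 0.3268 |

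At n = 100 the result crosses 0.10 between 9–1 and 8–2. At n = 75 it crosses between 8–2 and 7–3. In each setting, moving one case between arms can reverse the conclusion. This shows how fragile the test is; it does not estimate how many cases unblinding would move.

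**The case against.** **Visibility is not established.** A reader might infer that bedside staff can tell the arms apart. The documents do not support that. They do not say what port or seal the pouches have, whether a syringe entry leaves a mark, or in what state pouches reach the ICU. Nor do they describe placebo pouches as factory-sealed; that is inferred from the absence of a step in part B. This objection stands, and the point is limited to what staff could infer if entry is visible.

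**The blinding is not bare.** Section 5.4 does more than forbid discussion of the code, Section 5.5 delays the monitor's vial accountability until after unblinding, and the exchange preserves volume. All this is true, but none of it addresses pouch entry.

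**The conflict may be a copying error in Section 5.1.** The placebo block gives the dosage form as not applicable, yet asks for the expiry date of lyophilised material, which saline does not contain. The two-step wording may have been carried over from the active block in the same way. On that reading Appendix C is as intended and Section 5.1 needs the edit. This is plausible. It changes which text is wrong, but not the fact that entry is unmatched and unmasked.

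**Ascertainment is not wholly discretionary.** CPIS and quantitative aspirate culture are scheduled every third day, with a lung X-ray whenever possible. The panel receives all CPIS parameters and all X-rays, and local laboratory parameters are assessed blind (Sections 7.1.2, 7.2.3, 7.2.4 and 7.3). This narrows the route to bias considerably. The decision to perform BAL or PBS, the antibiotic choice and extubation still rest with the site.

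**Conclusion.** Two things are established from the text. Section 5.1 and Appendix C disagree on how placebo is prepared. In a double-blind trial, the written procedure also handles the pouches differently by arm, with no stated means of hiding it. Unblinding itself is not shown. It depends on the assumption that entry is visible on pouches each hospital buys locally, which may be true at some sites and not at others.

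The exposure is broad: up to 20 pouches per patient, in about 100 to 120 patients per arm at the upper recruitment figure (200 assessable or 240 recruited, halved). The size of any bias cannot be derived from the documents. A reader might put it at 10–20% of primary events by supposing that one or two of the 10 cases are affected, but that is only one or two divided by ten, and nothing supports that count. What can be said is that, with 10 events, one case can decide the primary test, so a cheap safeguard is worth having. This should be corrected, but as a possible and undemonstrated route to unblinding.

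**What to change.** Reconcile Sections 5.1 and 5.4 and Appendix C so that all three describe the same placebo preparation, and correct the lyophilised-material wording in the placebo block of Section 5.1.

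Amend Appendix C part B to mirror the pouch handling in part A: withdraw 3.0 mL and replace it with 3.0 mL of the same sterile 0.9% saline. State that the port is closed or sealed identically in both arms. The replacement fluid should be saline and not water for injection, because Sections 5.1 and 5.4 define placebo as 0.9% saline and water would create a new inconsistency. The matched exchange protects the blind whichever passage turns out to be the copying error.

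The active preparation, its volume and its concentration do not change. The cost is a short edit to the protocol, plus one syringe, about a minute of pharmacy time and one extra aseptic handling step per placebo pouch, and the same port closure or seal on every pouch in both arms.
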